We propose a 4-week, open-label, feasibility trial of adjunctive telmisartan in adult patients with TRS. We plan to recruit 10 patients. All patients will receive telmisartan 80mg daily for 4 weeks.

B. SPECIFIC AIMS

Primary

1. Evaluate changes in blood biomarkers for inflammation and oxidative stress.

C. STUDY DESIGN

Screening visit: After signing a HIPAA compliant informed consent form, subjects will undergo a review of medical history and concomitant medications, and a physical exam. The MINI International Neuropsychiatric Interview will be performed to confirm the psychiatric diagnosis. Subjects will also have a urine drug screen, urine pregnancy test, a complete blood count (CBC), complete metabolic panel (CMP), vital signs, 12-lead ECG.

Baseline visit: After the screening visit, eligible subjects will undergo: 1) vital signs; 2) efficacy assessment battery; 3) safety assessment battery; 4) blood biomarkers for inflammation and oxidative stress, including glutathione (GSH), glutathione disulfide (GSSG), high sensitivity C reactive protein (hsCRP), interleukin 6 (IL-6) and tumor necrosis factor α (TNF α).

Week 1, 2, 3 visits: Vital signs will be assessed. Treatment compliance and possible adverse effects will be evaluated. Subjects will receive one week supply of study medication. Urine drug screen will be repeated at week 2 only.

Week 4 visit: Subjects will undergo: 1) vital signs; 2) efficacy assessment battery; 3) safety assessment battery; 4) blood biomarkers for inflammation and oxidative stress, including GSH, GSSG, hsCRP, IL-6 and TNF α . Lab samples for CBC and CMP will also be collected.

Early termination visit: Subjects will undergo: 1) vital signs; 2) safety assessment battery; 3) CBC and CMP.

D. STUDY POPULATION

Subject eligibility

Inclusion Criteria

Each subject must meet all of the following criteria to be eligible for this study:

1. Age 18-65 years inclusive.
2. Primary diagnosis of Schizophrenia established by a structured psychiatric evaluation (MINI) based on Diagnostic and Statistical Manual of Mental Disorders Fifth Edition (DSM-V) criteria.
3. A Positive and Negative Syndrome Scale (PANSS) (Kay et al 1987) total score ≥ 70 with a score of ≥ 4 on two or more of the following PANSS items: delusions, conceptual disorganization, hallucinatory behavior, suspiciousness, and unusual thought content.
4. A score of ≥ 4 on the Clinical Global Impression—Severity (CGI-S) (Guy, 1976).

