5. Must have ongoing antipsychotic treatment for at least 8 weeks, with a stable dose for at least 4 weeks. Subjects who have failed to achieve clinically-recognized symptom reduction to at least 1 marketed antipsychotic agent, given at a Physician Desk Reference (PDR)-defined therapeutic dose for ≥ 8 weeks during the past 12 months, will be eligible.
6. Women of childbearing potential must have a negative pregnancy test performed at screening visit prior to randomization. Women enrolled in this trial must use adequate birth control.
7. Understands and is able, willing, and (in the opinion of the investigator) likely to fully comply with the study procedures and restrictions.

Exclusionary Criteria

Subjects who meet any of the following criteria will be excluded from the study:

1. Psychiatrically unstable.
2. Subjects with any clinically significant abnormalities as determined by medical history, physical exam, clinical and lab evaluation suggestive of an underlying disease state that may, in the opinion of the investigator, confound the results of study, increase risk to the subject, or lead to difficulty complying with the protocol.
3. Current insulin treatment for diabetes.
4. History of immunosuppression.
5. Current or recent radiation or chemotherapy treatment for cancer.
6. Chronic use of steroids (except local use or inhaler).
7. Pregnancy or breastfeeding.
8. Use of diuretics, ACE inhibitors, spironolactone, potassium supplements, digoxin or warfarin because of the possible drug-drug interaction with telmisartan.
9. Tested positive for the urine drug screen.

10. Subjects at imminent risk of suicide or injury to self or others, as per the opinion of the investigator, or history of significant suicide attempt within the last 6 months as per the Columbia Suicide Severity Rating Scale (C-SSRS).
11. Subjects that have taken an investigational drug or taken part in a clinical trial within 30 days prior to screening.
12. Subjects with a current (within the last 3 months) DSM-V diagnosis of alcohol or substance use disorder (excluding nicotine and caffeine) as established by the clinical assessment (MINI) at the screening visit will be excluded.
13. Any other reason that, in the opinion of the investigator, would compromise patient safety or integrity of the study.
14. Subjects with the lab values defined as exclusionary safety values in Table 1.

Table 1. Exclusionary Safety Values of Potential Clinical Concern

Complete Blood Count	

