Complete blood count (CBC): White blood cell (WBC) count with differential (absolute neutrophil count, lymphocytes, monocytes, basophils, and eosinophils), red blood cell (RBC) count, hemoglobin (Hgb), hematocrit (Hct), and platelet count.

Comprehensive metabolic panel (CMP): glucose, sodium, potassium, calcium, chloride, carbon dioxide, blood urea nitrogen (BUN), creatinine, calculated glomerular filtration rate, uric acid, phosphorus, magnesium, total protein, albumin, aspartate amino transferase (AST), alanine amino transferase (ALT), alkaline phosphatase (ALP), total bilirubin.

Blood levels of GSH, GSSG, hsCRP, IL-6, TNF α : Blood samples for GSH, GSSG, hsCRP, IL6 and TNF-alpha will be run at the UMass Memorial labs.

The PI, or medically qualified designee, should mark either “CS” for Clinically Significant or “NCS” for Not Clinically Significant in the margin of the laboratory result source document for items outside the normal range.

Urine drug screen: The test includes the following substances: opioids, cocaine, amphetamines, methadone, cannabinoids, barbiturates, benzodiazepines, methamphetamine, and phencyclidine.

Urine pregnancy test: The test will be performed in female subjects of childbearing potential using a dipstick urine test during the screening visit.

12-Lead Electrocardiogram (EGG)

A 12-lead ECG will be taken at following a supine rest for 5 minutes. The ECGs will be reviewed by the PI or medically qualified designee, and a cardiologist to assess any immediate abnormalities. The findings of the ECGs will be marked as normal, abnormal-not clinically significant, or abnormal-clinically significant.

Psychiatric diagnostic assessment

Mini International Neuropsychiatric Interview (MINI v7.0): The MINI 7.0 is a short clinician administered structured diagnostic interview for major psychiatric diagnoses in DSM-5 with an administration of around 20 minutes.

Efficacy assessment battery

The Positive and Negative Syndrome Scale (PANSS) (KAY ET AL 1987): The PANSS will be used to measure symptom severity in this trial. The PANSS is a 30-item questionnaire used to evaluate schizophrenia symptoms, based on the clinical interview as well as reports of family members or primary care hospital workers. The PANSS consists of Positive Symptom subscale (7 items), Negative Symptom subscale (7 items), and General Psychopathology subscale (16 items). Each item is scored on a 7-point scale with higher scores representing increasing levels

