When telmisartan was co-administered with digoxin, median increases in digoxin peak plasma concentration (49%) and in trough concentration (20%) were observed. It is therefore recommended that digoxin levels be monitored when initiating, adjusting, and discontinuing telmisartan. Telmisartan administered for 10 days slightly decreased the mean warfarin trough plasma concentration; this decrease did not result in a change in International Normalized Ratio (INR). Telmisartan can cause fetal and neonatal morbidity and death when administered to pregnant women. In volume- and/or salt-depleted patients (e.g., those being treated with high doses of diuretics), symptomatic hypotension may occur after initiation of therapy with telmisartan. Adverse events occurring at an incidence of 1% or more in patients treated with telmisartan and at a greater rate than in patients treated with placebo, irrespective of their causal association, include upper respiratory tract infection, back pain, sinusitis, diarrhea and pharyngitis. Common adverse experiences have generally been mild and transient in nature and have only infrequently required discontinuation of therapy. In placebo-controlled trials involving 1,041 patients treated with various doses of telmisartan (20-160mg) monotherapy for up to 12 weeks, an overall incidence of adverse events similar to that of placebo was observed. (Micardis® package insert, revised, February 2018).

For the proposed study, patients will be excluded if they are on diuretics, ACE inhibitors, digoxin or warfarin because the possible drug-drug interaction with telmisartan. Subjects will be excluded from the study if they have an abnormal potassium blood level out of the defined cutoff range at screening. Subjects will be terminated from the study if they have an abnormal potassium blood level at screening. For female patients of childbearing potential, a urine pregnancy test must be negative at screening. These patients must agree to practice appropriate birth control methods during the study.

Discontinuation from Study Treatment

The reasons for early discontinuation include the following: 1) request of patient, 2) decision of the PI, 3) serious adverse event.

Procedures for discontinuation from study

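### The only scheduled pregnancy test is the Screening dipstick, although the protocol says telmisartan can cause fetal death; none is repeated at Baseline before first dispensing or during dosing

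*Protocol*

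**What the plan says.** The hazard is stated in Protocol Section F, under the potential risks of telmisartan: "Telmisartan can cause fetal and neonatal morbidity and death when administered to pregnant women".

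Every mention of the pregnancy test puts it at Screening:

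- Section E, Laboratory assays: "The test will be performed in female subjects of childbearing potential using a dipstick urine test during the screening visit".
- Section D, inclusion criterion 6: "Women of childbearing potential must have a negative pregnancy test performed at screening visit prior to randomization". The SAP's Participants section repeats this almost word for word.
- Section F: "For female patients of childbearing potential, a urine pregnancy test must be negative at screening".
- Section C and the SAP's Procedures list the test among the Screening procedures and at no other visit.
- The Schedule of Events marks it once, under Screening.

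The Schedule of Events marks drug dispensing at Baseline and at Visits 1, 2 and 3. Section C places Baseline after Screening without saying how soon, and the schedule gives Screening no study week.

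The plan does contain safeguards. Exclusion criterion 7 reads "Pregnancy or breastfeeding". Contraception is required twice: "Women enrolled in this trial must use adequate birth control" (Section D) and "These patients must agree to practice appropriate birth control methods during the study" (Section F). Adverse events are reviewed at each visit (Section E), and the investigator may stop treatment (Section F).

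**The concern.** The plan names a severe fetal hazard and then relies on one negative dipstick of unspecified age. A woman who conceives shortly before Screening, too early for the dipstick to show it, or between Screening and Baseline, could start telmisartan and continue it for four weeks without anyone knowing.

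The wording of inclusion criterion 6 does not close the gap. It times the test relative to randomization, but this is a single-arm trial in which every patient receives telmisartan. The phrase is a leftover. It does not move the test to after the first dose, but it does not tie the test to first dispensing either.

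What is at stake is the safety of a few participants. Neither the estimates nor the tests in the analysis depend on it.

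**Working it through.** The plan gives no figure to reproduce here. The check counts scheduled tests against scheduled dispensings, then asks what an added test could detect.

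**Step 1: count from the Schedule of Events.** There is 1 pregnancy test (Screening) and there are 4 dispensings (Baseline, Visits 1, 2, 3). Dispensings with a test at the same visit: 0 of 4. Tests at Week 4 or Early Termination: 0. The text of Sections C, D, E and F agrees with the table, so the count does not depend on how the table was extracted.

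**Step 2: drug supply that a test would precede.** Each supply covers one week, so 4 × 7 = 28 days.

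- Baseline test: precedes 4 of 4 supplies, 28 of 28 days.
- Visit 2 test: precedes the supplies given at Visits 2 and 3, 2 × 7 = 14 of 28 days.

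These figures count drug supply, not fetal risk. The documents give no gestational timing or dose relation.

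**Step 3: which conceptions each test could find.** Two inputs are not in the documents and are assumed:

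- L, days from conception to a positive dipstick: 7 to 14.
- G, days from Screening to Baseline: shown at 0, 7, 14 and 28.

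Set Baseline and the first dose at day 0, Screening at day −G and Visit 2 at day 14. A test on day t finds conceptions up to day t − L.

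- Screening finds conceptions up to day −G − L. Those from then until the first dose, a window of G + L days, are missed by the plan as written.
- Baseline finds conceptions up to day −L. Newly covered: (−L) − (−G − L) = G days, whatever L is.
- Visit 2 finds conceptions up to day 14 − L. Newly covered beyond Baseline: (14 − L) − (−L) = 14 days.

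Pre-dose conception window left undetected, in days:

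| G | As written, L = 7 | As written, L = 14 | With Baseline test | With Baseline and Visit 2 tests |
|---|---|---|---|---|
| 0 | 7 | 14 | 7 to 14 | 0 |
| 7 | 14 | 21 | 7 to 14 | 0 |
| 14 | 21 | 28 | 7 to 14 | 0 |
| 28 | 35 | 42 | 7 to 14 | 0 |

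The last column is zero because 14 − L is at least 0 throughout the assumed range. A pregnancy first found at Visit 2 would already have had up to 14 days of drug.

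**Step 4: conceptions during dosing.** Visit 2 reaches dosing day 7 if L = 7, and day 0 if L = 14. Conceptions on the remaining 28 − 7 = 21 to 28 − 0 = 28 of the 28 dosing days are found by neither test. A test at Week 4 (day 28) would reach day 28 − 7 = 21 or day 28 − 14 = 14, but after the last supply has been given.

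**The case against.** The strongest case accepts the facts and disputes their weight. Only 10 patients are planned, the number of women of childbearing potential among them is not given, and dosing lasts four weeks. A negative test and contraception are both mandatory.

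Exclusion criterion 7 is not limited to Screening or to pregnancies already known. Because PANSS and CGI-S are entry criteria first scheduled at Baseline, eligibility cannot be complete before Baseline, and the exclusion still applies there. Visits are weekly with adverse-event review, medical history is to be updated throughout, and the investigator monitors safety continuously, so a missed period could prompt a test. The documents set no retest frequency. A Visit 2 test would miss most conceptions that occur during dosing. Consent pages are not in the documents supplied, so instructions given to participants cannot be judged.

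Much of this stands, and it keeps the priority modest. It does not remove the gap. Contraception and exclusion 7 prevent or prohibit, but neither detects. Adverse-event review and history updates depend on someone noticing something, and an unrecognised pregnancy is by definition not noticed. The reason for a Visit 2 test is not chiefly conception during dosing: it finds conceptions in the last L days before the first dose, which a Baseline dipstick is too early to show. If Screening and Baseline fall on the same day (G = 0), the Baseline test adds nothing and Visit 2 supplies all the gain.

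**Conclusion.** The concern holds. Pregnancy is tested once, at Screening, with 0 of 4 dispensings accompanied by a test and no limit on the age of the negative result at first dose. As written, a pre-dose conception window of G + L days goes undetected: 7 to 14 days if Baseline falls on the day of Screening, and 35 to 42 days if it falls 28 days later. These lengths rest on the assumed 7 to 14 days to a positive dipstick and on an interval that the protocol does not set. They describe when a conception would be missed, not how likely it is. The likelihood is low, given the required contraception and the small sample, and cannot be computed from the documents.

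The change should be made because the harm is severe by the protocol's own account and the remedy is cheap. It is a safety improvement with no bearing on the statistical analysis.

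**What to change.** In Protocol Sections C and E and the Schedule of Events, add a urine dipstick for women of childbearing potential:

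1. At Baseline, with a negative result required before first dispensing. This makes the result current at the first dose, so a separate limit on the Screening-to-Baseline interval is not essential.
2. At Visit 2, on the urine already collected for the drug screen, read before that week's supply is given.

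State that no further drug is dispensed after a positive result. Reword inclusion criterion 6 and the matching sentence in Section F to require a negative test at Screening and again at Baseline before first dispensing, and drop the reference to randomization. Make the same edit to the SAP's Participants section for consistency only.

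Optional: a test at Visit 4 or Early Termination, with follow-up of any pregnancy to outcome. This would reach some of the later conceptions that the two added tests miss.

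Cost: at most 2 × 10 = 20 dipsticks, if all 10 patients were women of childbearing potential; one brief urine collection at Baseline; and a minor amendment. There are no added visits and no effect on sample size or analysis.

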of psychopathology: 1) Absent, 2) Minimal, 3) Mild, 4) Moderate, 5) Moderate severe, 6) Severe, and 7) Extreme.

Scale for Assessment of Negative Symptoms (SANS) (Andreasen 1989): The SANS assesses 5 domains: affective flattening, alogia, avolition/apathy, anhedonia/asociality, and attention. Within each domain, separate symptoms are related from 0 (absent) to 5 (severe).

Clinical Global Impressions–Severity (CGI-S) and Clinical Global Impressions–Improvement (CGI-I) Scales (Guy, 1976): The CGI-S is an observer-rated scale that measures illness severity. The severity is measured using a 7 point Likert scale: 1) Normal, not at all ill, 2) Borderline mentally ill, 3) Mildly ill, 4) Moderately ill, 5) Markedly ill, 6) Severely ill, and 7) Among the most extremely ill patient. The CGI-I is an observer-rated scale that measures illness improvement. Improvement is measured using a 7 point Likert scale: 1) Very much improved, 2) Much improved, 3) Minimally improved, 4) No change 5) Minimally worse, 6) Much worse, 7) Very much worse.

Safety assessment battery

Adverse Events (AE): Adverse events will be monitored at each study visit. The PI or medically qualified designee will review adverse events at every study visit. AE information is collected and recorded starting on the day the consent is signed until the end of an individual’s participation in the study.

The Columbia Suicide Severity Rating Scale (C-SSRS) (Posner et al 2007): The C-SSRS is a low-burden measure of the spectrum of suicidal ideation and behavior that was developed in the National Institute of Mental Health Treatment of Adolescent Suicide Attempters Study to assess severity and track suicidal events through any treatment. It is a clinical interview providing a summary of both ideation and behavior that can be administered during any evaluation or risk assessment to identify the level and type of suicidality present. The C-SSRS can also be used during treatment to monitor for clinical worsening. The C-SSRS will be performed to assess suicidal ideation and behavior. It contains a 1-to-5 rating scale for suicidal ideation of increasing severity (from a “wish list to die” to an “active thought of killing oneself with plan and intent”). The time frame is the past six months for the Baseline/Screening scale and since the last visit for the Since Last Visit scale.

Monitoring and Reporting of Adverse Events

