Continuous data and safety monitoring will be conducted by the PI. Any adverse effect reported to study personnel will be reviewed with the PI or sub-investigator who will determine whether they are mild, moderate or severe and the likelihood (definitely/possible/probable) that it is related to the study medication. All AEs will be followed until resolution, until deemed stable by the investigator or until the subject is deemed by the investigator to be lost to follow-up

Intensity	Definition
Mild	Causes transient or mild discomfort ; no limitation of usual activities; no medical intervention required.
Moderate	Causes mild to moderate limitation in activity; some limitation of usual activities: no or minimal medical intervention or therapy is required.
Severe	Causes marked limitation in activity; some assistance is usually required; medical intervention or therapy is required; hospitalization is probable.

The PI is ultimately responsible for assessing and reporting all adverse events as outlined in the study plan. The assessment of AEs may be delegated to a medically qualified Sub-Investigator, trained on this study plan. The PI will report adverse events to the IRB in accordance with IRB guidelines.

Reporting of Serious Adverse Events

The PI will report all SAEs to UMass IRB. The PI will inform the IRB regarding any AE (does not have to be causally related) that is both serious and unexpected; or that represents a series of AEs that, on analysis, is unanticipated, or occurs at an unanticipated frequency, or otherwise represents an unanticipated safety risk to the study subject in accordance with UMass IRB reporting guidelines.

F. TREATMENT

Dosing

Subjects will start telmisartan 40mg once a day during week 1; the dose will be increased to 80mg (target dose) or as tolerated during the remaining weeks.

Study medication Supplies and Administration

Telmisartan has 20mg, 40mg and 80mg dose strengths. Subjects will be given one 40mg pill per day during week 1, and one 40mg pill plus two 20mg pills per day for the remaining weeks.

Potential risks of telmisartan

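### The adverse-event causality scale has no unlikely or not-related level, so an event judged unrelated to telmisartan, including one before the first dose, has no valid rating

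*Protocol*

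**What the plan says.** Protocol Section E, under Monitoring and Reporting of Adverse Events, sets the rating rule. "Any adverse effect reported to study personnel will be reviewed with the PI or sub-investigator", who grades intensity and determines "the likelihood (definitely/possible/probable) that it is related to the study medication". A table directly below defines the intensity grades. The three causality terms are not defined, and no further level appears anywhere in the protocol or the SAP.

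Four other places bear on the point:

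- **Section E, Safety assessment battery:** "AE information is collected and recorded starting on the day the consent is signed until the end of an individual’s participation in the study".
- **Section E, Reporting of Serious Adverse Events:** "The PI will report all SAEs to UMass IRB". The Institutional Review Board (IRB) is also told of "any AE (does not have to be causally related) that is both serious and unexpected".
- **Section F, Procedures for discontinuation from study:** a patient who leaves before receiving any study treatment is asked back for a final visit that includes an adverse-event assessment.
- **Section F, Potential risks of telmisartan:** in earlier placebo-controlled monotherapy trials, "an overall incidence of adverse events similar to that of placebo was observed".

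**The concern.** A causality scale should be able to record every answer the assessor might reach. This one cannot record that an event had nothing to do with the drug. The protocol accepts that such events occur, and it collects events at times when the drug cannot have caused them.

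The trial is open-label with a single arm, so there is no comparator against which to judge background events. A reader of its tolerability results would naturally look at the investigator's attribution. If the lowest available rating is *possible*, that attribution no longer separates related from unrelated events. Because the rating is made when the event is reviewed, a missing level is hard to restore reliably afterwards. Section H says the study is meant to inform the design of future studies, and a tolerability statement carried forward from it would inherit the problem.

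**Working it through.** The plan states no figure on this point to reproduce, so the check is mainly textual.

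**Step 1. What the scale can record.** It has three levels: definitely, probable and possible. Let D, Pr and Po be the numbers of events at each level, and N the number rated. If the list is applied as written, D + Pr + Po = N, so the share rated at least *possible* is N/N = 100%, whatever the true causes.

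**Step 2. Whether the protocol produces events that do not fit.** It does, in three ways that need no assumption about background rates.

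- *Events before the first dose.* Section E starts recording at consent. The Schedule of Events starts its adverse-event row at Baseline, the visit at which drug is first dispensed. On either reading, events that precede the first dose can be recorded. Section E also requires clinically significant vital-sign findings to be captured as adverse events, and vital signs are taken at Screening and Baseline.
- *Patients never dosed.* The clause in Section F on leaving before treatment refers to randomization, which this trial does not have. Its substance is still clear: events are assessed in people who took no study drug, and the lowest listed rating for them is *possible*.
- *Events accepted as unrelated.* The serious-event paragraph expressly covers events without a causal link. The rating sentence gives no way to record one.

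**Step 3. Where the rating is used.** Each place where causality might enter, set against what the text says:

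| Use | Rule in the documents | Depends on the causality rating? |
|---|---|---|
| Recording of events | From consent to end of participation (Section E) | No |
| Follow-up of events | All events, to resolution, stability or loss to follow-up (Section E) | No |
| Serious events to the IRB | All of them (Section E) | No |
| Serious and unexpected events to the IRB | Causal link expressly not required (Section E) | No |
| Discontinuation | Patient request, PI decision, or "3) serious adverse event" (Section F) | No relatedness condition |
| Protocol analysis | Paired t tests and correlations (Section H) | No |
| SAP analysis | A paired t-test | No |

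Neither analysis section plans a count of adverse events by relatedness, and the primary aim in Section B concerns blood biomarkers.

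**Step 4. Size.** If a drug-related count were made on the literal scale, and a share u of events were truly unrelated, the count would be overstated by the factor 1/(1 − u). The documents give no value for u. At u = 0 the factor is 1, and it grows without limit as u approaches 1. For illustration only, an assumed u of 0.3 gives 1/0.7 = 1.43, and an assumed u of 0.7 gives 1/0.3 = 3.33. The similar-to-placebo statement in Section F does not supply u: it gives no rates, and it concerns monotherapy, whereas here telmisartan is added to antipsychotic treatment.

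**The case against.** The strongest reply is that nothing in the plan uses the rating. Step 3 bears this out. Extra levels would leave the number of events, the number of serious events and their intensity unchanged. A reader might infer from the missing levels that the trial's safety result is biased by construction. The documents do not support that, because they plan no safety result by relatedness and there is no second arm whose comparison could be distorted.

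A reader might also infer that the causality rating is the only way the trial can tell drug effects from background. That goes too far. Vital signs, including supine-to-standing blood pressure, are taken from Screening to Week 4, and blood counts and metabolic panels at Screening and Week 4. These allow within-patient comparisons before and on treatment. A fixed multiplier such as 1.4 to 3.3 is equally unsupported, since it rests wholly on an assumed share. It also collapses three levels into one, whereas a report by level would keep some gradient between *definitely* and *possible*.

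It can further be said that the bracketed list is not declared exhaustive, that no one is told to attribute an event before dosing to the drug, and that the event form, which is not among the documents, may already have a *not related* box. These points limit the certainty of the harm but do not remove the gap. Nothing marks the list as illustrative. Assessment may be delegated, so different assessors could improvise differently. An unwritten option is not a rule.

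**Conclusion.** The gap is real and minor. As written, the scale has no valid rating for an event judged unrelated, and applied literally it records such an event as at least *possible*. For events before the first dose or in never-dosed patients, that is a misclassification, so this is more than missing detail.

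The effect is confined to the causality rating itself and to any later summary of drug-related events from these 10 patients. Its direction is toward attribution to telmisartan. Its amount cannot be computed from the documents. All-cause and serious event counts, reports of serious events, discontinuation and the planned t tests stand as they are.

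The conclusion assumes that the listed levels are applied as written and that the event form offers no others. If the form already has a *not related* option, the protocol text should be brought into line with it.

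**What to change.** 1. In Section E, extend the causality scale with *unlikely* and *not related*, and make the same change on the adverse-event form if it lacks them. A short definition of each level, to match the intensity table, would help assessors apply the scale consistently.
2. State that events with onset before the first dose, including all events in patients never dosed, are classified as not related to study medication.
3. Add to the analysis section that adverse events will be reported at every causality level, alongside the all-cause count.

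The cost is one line of text for the scale, brief wording for the other two items, and a small form change. No dose, visit, reporting duty or planned test is altered.
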